## 2.7 Analyses of safety endpoints

All safety analyses will be based on the safety set. Only those visits that were pre-planned in the protocol will be reported in tables for safety variables.

Analysis of adverse events will be based on treatment emergent events, which are defined as events started on or after the first dose of study treatment or events present prior to the first dose of study treatment but increased in severity based on preferred term and on or before last dose + 84 days.

Other safety variables including LAB, Vitals will be evaluated based on on-treatment events, which are defined as any events that happened after first dose of study treatment and on or before last dose +84 days.

Safety analysis will be performed on actual treatment, for patients in any of the three cohorts and in each of the three cohorts, respectively. Analyses will be presented by Treatment Period 1 and entire treatment period and by treatment groups as specified in [Table 2-1](#).

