Treatment blinding is maintained beyond the primary endpoint (week 16) throughout Treatment Period 2, which enables cross-comparison of the sequential efficacy and safety data of the 2-weekly dosing regimen in Treatment Period 2 to the 4-weekly dosing regimen in Treatment Period 1. Furthermore, it ensures that investigators remain blinded regarding the treatment subjects received during Treatment Period 1. In addition, continued blinding ensures more objective efficacy and safety assessment during Treatment Period 2.

An 8-week follow-up period will enable the assessment of disease activity [REDACTED] after the end of treatment.

The regular assessments of disease activity and clinical status ensure that safety is monitored closely and that both, subjects and investigators, have the opportunity to assess if the continued participation in the trial is to the patient's benefit. If the subject's participation is deemed not to be of benefit for the subject, she/he can exit the trial at any time.

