#### **Treatment Period 2: Weeks 16-32**

- Patients in the active **secukinumab 300 mg every 4 weeks treatment arm** stay on secukinumab 300 mg every 4 weeks, meaning they receive secukinumab 300 mg s.c. at Weeks 16, 20, 24 and 28. In order to maintain the blinding they additionally receive placebo injections at Weeks 17, 18 and 19 as well as placebo injections at Weeks 22, 26 and 30.
- Patients from the **placebo with switch to secukinumab 300 mg every 2 weeks treatment arm** switch over to active secukinumab 300 mg every 2 weeks treatment. They receive a weekly induction with secukinumab 300 mg s.c. at Weeks 16, 17, 18, 19 and 20 and then secukinumab 300 mg every 2 weeks, meaning at Weeks 22, 24, 26, 28 and 30.

The first injection of Treatment Period 2 is given at Week 16. The last injection (secukinumab 300 mg or placebo) is given in both the treatment arms **at week 30**.

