Period	Treatment Period 2										Notes
Visit Name	Week 17	Week 18	Week 19	Week 20	Week 22	Week 24	Week 26	Week 28	Week 30	Week 32	
Visit Numbers 	170	180	190	200	210	220	230	240	250	1999	
Days	120	127	134	141	155	169	183	197	211	225	
Hematology						X				X	
Clinical chemistry						X				X	
Urine pregnancy test (local)										S 	
Pregnancy test (serum)										S	
Skin biopsy 											
Mucosal biopsy 											
Scalp biopsy 										X 	
Contact IRT				S 		S 		S 		S 	
Drug administration				X 		X 		X 			
Home administration 	X 	X 	X 		X 		X 		X 		

 For all patients in the LPP cohort.

 For all patients in the MLP cohort who have an oral affection of the disease.

 Not to be done if EOT already happened.

 For all patients in the CLP cohort.

 For all patients in the MLP cohort.

 These injections will be self-administered at home by the patient, unless a preference for office-administration is expressed

Period	Follow-up		Unplanned	Notes
Visit Name	Week 36	Week 40	Unscheduled 	
Visit Numbers 			260	
Days	253	281	-	
Concomitant medications	update as necessary		X	Assessment to be recorded in the clinical database or received electronically from a vendor
Prior or concomitant non-drug therapies/procedures	update as necessary		S	Assessment to be recorded in the source documentation only
Adverse Events	update as necessary			 Visit structure given for internal programming purpose only
Vital Signs		X	X	 For all patients in the CLP cohort. Additionally for patients in the MLP cohort who have a concomitant cutaneous affection.
Body Height				 For all patients in the MLP cohort who have an oral affection of the disease. Additionally for patients in the CLP cohort who have a concomitant oral affection.
Body Weight		X	X	
Physical Examination			S	
Hepatitis screen				 For all patients in the LPP cohort.
Tuberculosis test			S	 For all patients in the MLP cohort who have an oral affection of the disease.
Investigator's Global Assessment (IGA)	X	X	X	 For all patients in the CLP cohort.

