## 8.4 Safety/Tolerability

All blood draws and safety assessments should be done prior to study treatment administration. Appropriate safety assessments (e.g., evaluation of AEs and SAEs) should be repeated after the dose is administered.

Safety assessments are specified below with the assessment schedule detailing when each assessment is to be performed.

In the event of a major health care disruption (e.g., pandemic, epidemic) that limits or prevents on-site study visits, regular phone will occur (every 4 weeks or more frequently if needed) for safety monitoring and discussion of the patient's health status until the patient can again visit the site. Events qualifying for being reported in the CRF (e.g., AE, procedure) should be entered as appropriate. If patients cannot visit the site to have urine pregnancy tests done, the urine pregnancy test kits can be provided to the patient or shipped directly to the patient's home (e.g., together with the study drug). After appropriate instruction, patients can perform the urine pregnancy test at home and report the result to the site. It is important that patients do the pregnancy test first and only if the test result is negative proceed with the administration of the study drug.

For details on AE collection and reporting, refer to [Section 10.1.1](#).

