## **10 Safety monitoring and reporting**

### **10.1 Definition of adverse events and reporting requirements**

#### **10.1.1 Adverse events**

An adverse event (AE) is any untoward medical occurrence (e.g., any unfavorable and unintended sign [including abnormal laboratory findings], symptom or disease) in a subject or clinical investigation subject after providing written informed consent for participation in the study. Therefore, an AE may or may not be temporally or causally associated with the use of a medicinal (investigational) product.

In addition, all reports of intentional misuse and abuse of the product are also considered an adverse event irrespective of whether a clinical event has occurred.

The investigator has the responsibility for managing the safety of individual subject and identifying adverse events.

Novartis qualified medical personnel will be readily available to advise on trial related medical questions or problems.

The occurrence of adverse events must be sought by non-directive questioning of the subject at each visit during the study. Adverse events also may be detected when they are volunteered by the subject during or between visits or through physical examination findings, laboratory test findings, or other assessments.

Adverse events must be recorded in the Adverse Events eCRF under the signs, symptoms or diagnosis associated with them, accompanied by the following information (as far as possible) (if the event is serious refer to [Section 10.1.2](#)):

1. The severity grade.
  - mild: usually transient in nature and generally not interfering with normal activities
  - moderate: sufficiently discomforting to interfere with normal activities
  - severe: prevents normal activities
2. Its relationship to the study treatment (suspected: Yes/No). If the event is due to lack of efficacy or progression of underlying illness (i.e. progression of the study indication), the assessment of causality will usually be 'Not suspected'. The rationale for this guidance is that the symptoms of a lack of efficacy or progression of underlying illness are not caused by the trial drug, they happen in spite of its administration and/or both lack of efficacy and progression

of underlying disease can only be evaluated meaningfully by an analysis of cohorts, not on a single subject.

3. Its duration (start and end dates) or if the event is ongoing, an outcome of not recovered/not resolved must be reported.

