## **2.2 Analysis sets**

The following analysis sets will be used for the data analysis. Rules of exclusion criteria of analysis are detailed in [Section 5.6](#).

The **Randomized Analysis Set (RAS)** consists of all randomized subjects. Subjects will be analyzed according to the treatment assigned at randomization.

The **Full Analysis Set (FAS)** comprises all subjects to whom study treatment has been assigned. Subjects will be analyzed according to the treatment assigned to at randomization. Mis-randomized subjects (mis-randomized in IRT) will be excluded from FAS. Mis-randomized subjects are defined as cases where IRT contacts were made by the site either prematurely or

inappropriately prior to confirmation of the subject's final randomization eligibility and no study medication was administered to the subject.

The **Safety Set** includes all subjects who received at least one dose of study treatment. Subjects will be analyzed according to the study treatment received, where treatment received is defined as the randomized/assigned treatment if the subject took at least one dose of that treatment or the first treatment received if the randomized/assigned treatment was never received.

The summary statistics analyses in this study will be performed according to domains with respective specifications of analyses sets, analyses period and treatment groups ([Table 2-1](#)).

**Table 2-1** Summary statistics specifications

Domains	Analyses sets	Analysis Period	Treatment group labels for each analysis period
Patient disposition, Demographics, Other baseline characteristics *	RAS	Treatment Period 1	Secukinumab 300 mg Q4W Placebo Total
		Treatment Period 2 Follow up (only for disposition tables)	Secukinumab 300 mg Q4W Secukinumab 300 mg Q2W Total
Efficacy endpoints	FAS	Treatment Period 1	Secukinumab 300 mg Q4W Placebo
		Entire treatment period	Secukinumab 300 mg Q4W Placebo Placebo-Secukinumab 300 mg Q2W
Safety data (Number of doses, duration of exposure, prior and concomitant therapies, concomitant medical procedures, significant non-drug therapies, laboratory data, AEs, etc.)	Safety set	Treatment Period 1	Secukinumab 300 mg Q4W Placebo
		Entire treatment period	Secukinumab 300 mg Q4W Secukinumab 300 mg Q2W Placebo Any Secukinumab

\* Treatment groups for protocol deviations for entire treatment period: AIN457 300 mg Q4W, AIN457 300 mg Q2W, Any AIN457 300 mg, Placebo, Total

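### No Treatment Period 2 safety table is planned, so Q2W adverse events appear only beside an entire-period Q4W column that runs longer and mixes two visit schedules

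*SAP*

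**What the plan says.** SAP 2.7 fixes the safety reporting windows: "Analyses will be presented by Treatment Period 1 and entire treatment period and by treatment groups as specified in" Table 2-1. The safety row of Table 2-1 has Treatment Period 1 (Q4W, placebo) and the entire treatment period, with columns "Secukinumab 300 mg Q4W Secukinumab 300 mg Q2W Placebo Any Secukinumab". Table 2-6 uses the same two windows. For the entire period it adds exposure-adjusted rates for AEs, SAEs, related AEs, deaths and other significant AEs. AEs by severity and notable laboratory or vital-sign values get crude incidence only. Table 2-1 does use Treatment Period 2 as a window, but not for safety.

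Protocol 4.1 gives the assessment of the 2-weekly regimen's safety as one purpose of Treatment Period 2, and says that continued blinding "enables cross-comparison of the sequential efficacy and safety data of the 2-weekly dosing regimen in Treatment Period 2 to the 4-weekly dosing regimen" used in Treatment Period 1.

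AEs are collected mainly at visits. Protocol 10.1.1: "The occurrence of adverse events must be sought by non-directive questioning of the subject at each visit during the study". Protocol 8.4: "Appropriate safety assessments (e.g., evaluation of AEs and SAEs) should be repeated after the dose is administered". Period 1 doses are given at site, with a pandemic exception. In Period 2, Table 8-1 marks Weeks 17, 18, 19, 22, 26 and 30 as home injections in both arms: "These injections will be self-administered at home by the patient, unless a preference for office-administration is expressed".

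**The concern.** Q2W is the higher regimen and, according to Protocol 4.6, not an approved one, so readers will look closely at its AE column. That column appears only in a table whose neighbours were collected differently. Q4W has a longer follow-up and includes a month of weekly site visits. Placebo comes from Period 1, with site dosing by default. With equal true risk, shorter follow-up and sparser questioning would both tend to lower the Q2W figure.

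The database will hold a window, Weeks 16 to 32, in which both arms have the same length of observation, the same scheduled visits and the same injection weeks. No AE-incidence or notable-abnormality table isolates it.

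**Working it through.** **Check on the plan's own figure.** Active Q4W doses: Weeks 0, 1, 2, 3, 4, 8, 12 (7) plus Weeks 16, 20, 24, 28 (4) = 11; 11 × 300 mg = 3300 mg. Active Q2W doses: "weekly induction with secukinumab 300 mg s.c. at Weeks 16, 17, 18, 19 and 20 and then secukinumab 300 mg every 2 weeks", giving Weeks 16 to 20 weekly (5) plus Weeks 22, 24, 26, 28, 30 (5) = 10; 10 × 300 mg = 3000 mg. The difference is 300/3000 = 10%. All three figures match Protocol 4.4, so the dose counts are sound.

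**Home doses.** Crossing these weeks with the home weeks in Table 8-1:
- Q2W active doses at home by default: Weeks 17, 18, 19, 22, 26, 30 = 6 of 10.
- Q4W active doses at home: 0 of 11. That arm takes placebo on the same six weeks, so 6 of its 7 + 10 = 17 injections are at home.
- Period 1 placebo doses at home: 0 of 7.

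**Site visits after first dose.** Period 1: Weeks 1, 2, 3, 4, 8, 12, 16 = 7. Period 2: Weeks 20, 24, 28, 32 = 4. Follow-up: Weeks 36, 40 = 2. In the induction month alone there are 4 in Period 1 and 1 in Period 2.

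| Entire-period column | Window | Weeks | Site visits | Visits per week |
|---|---|---|---|---|
| Q4W | Weeks 0–40 | 40 | 7 + 4 + 2 = 13 | 13/40 = 0.33 |
| Q2W | Weeks 16–40 | 24 | 4 + 2 = 6 | 6/24 = 0.25 |
| Placebo | essentially Weeks 0–16 | 16 | 7 | 7/16 = 0.44 |

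The Week 40 end follows from SAP 2.4.1. Exposure stops at the earlier of the last visit and last dose plus 84 days; the last injection at Week 30 plus 12 weeks is Week 42, so the Week 40 visit comes first.

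**Crude incidence over unequal windows (illustration).** Assume the same constant hazard in both regimens and complete follow-up. If the 24-week risk is p, the 40-week risk is 1 − (1 − p)^(40/24). For p = 10%, 30% and 50% this gives 16%, 45% and 69%. AEs by severity and notables have no planned rate that would remove this difference.

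**What a Weeks 16–32 window equalises.** Both arms have 16 weeks, site visits at Weeks 16, 20, 24, 28 and 32, and the same 10 injection weeks.

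**What it does not equalise.** All 4 active Q4W doses in Period 2 are at site, while 6 of 10 active Q2W doses are at home by default; the Q4W home injections are placebo. Ascertainment on active-dose days therefore still differs.

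**Precision of the added table.** Half-width = 1.96 × √[p(1 − p)(1/n₁ + 1/n₂)]. Pooled over cohorts, n₁ = 3 × 24 = 72 and n₂ = 3 × 12 = 36. At p = 30%: 1.96 × √[0.21 × (1/72 + 1/36)] = 0.183, about 18 points. At 10% and 50% it is 12 and 20 points. With assumed losses to 58 and 25 it is about 14, 22 and 23 points at 10%, 30% and 50%; per cohort (24 and 12) it is 21, 32 and 35 points.

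**The case against.** The strongest reply is that the planned Q2W-versus-Q4W comparison is less unequal than it looks. A reader might infer that Q2W harms are set against Q4W data collected wholly at weekly, site-dosed visits. The documents do not support that. The only planned safety tables with both regimens are the entire-period ones, whose Q4W column includes Period 2 with its 4-weekly visits and six home injections. The Protocol 4.1 sentence is a rationale for blinding, not an SAP table.

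A rough model agrees. Suppose a short AE is recalled only at the next site visit, with recall halving every h weeks and no self-report. Mean capture over a gap of g weeks is (1 − e^(−λg))/(λg), with λ = ln 2/h. At h = 2 this is 0.845 for a 1-week gap and 0.541 for a 4-week gap. Q4W over 40 weeks captures (4 × 0.845 + 36 × 0.541)/40 = 0.571 and Q2W captures 0.541: a ratio of about 0.95 (0.90 to 0.99 for h from 1 to 8 weeks). The half-life is assumed. Self-report would narrow the gap further: Table 8-1 footnote 2 asks the investigator to collect AEs from home administrations, and Protocol 6.7.2 tells patients to contact the site. No contact schedule is set for this, apart from calls during a health-care disruption.

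A reader might also infer that the regimens are never shown concurrently. They are, for laboratory and vital-sign changes by visit (SAP 2.7.3 and 2.7.4.1).

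Finally, the Period 2 table has biases of its own. Q2W patients are newly exposed and in induction, while Q4W patients have already tolerated 16 weeks. Placebo patients in remission at Week 16 do not enter Period 2, and Period 1 dropouts are missing from both columns. Protocol 4.1 concedes some unblinding of remitters who continue.

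All of this stands. It limits what the added table can show, but it does not supply the missing AE and notable-abnormality tabulation.

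**Conclusion.** The point holds as a gap in reporting. SAP 2.7, Table 2-1 and Table 2-6 contain no Treatment Period 2 safety tabulation, although Q2W begins only in that period and its safety is a stated reason for it. The entire-period table sets 24 weeks of Q2W beside up to 40 weeks of Q4W and essentially 16 of placebo, with 0.25, 0.33 and 0.44 scheduled site visits per week. The loss of AE capture against the Q4W column is probably modest. Unequal follow-up matters more for the outputs reported as crude incidence only.

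A reader might go further and treat the Period 2 table as free of ascertainment bias, or as the preferred comparison. Neither follows: active-dose-day ascertainment still differs, and stage of exposure is confounded with regimen. The table would be descriptive, and it has no placebo column, so the placebo contrast is helped only by a footnote.

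This is a cheap improvement, not a defect that invalidates the safety analysis. It rests on the default schedule (site dosing can be requested in Period 2, and Period 1 has a pandemic exception) and on the unredacted SAP text; some SAP sections are redacted and could not be checked.

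**What to change.** - In the safety row of SAP Table 2-1, in SAP 2.7 and in Table 2-6, add a descriptive Treatment Period 2 window with columns Secukinumab 300 mg Q4W and Secukinumab 300 mg Q2W. It would cover AEs starting on or after the Week 16 dose and up to Week 32, and notable laboratory and vital-sign values in the same window. Place it beside the existing tables and the Protocol 4.1 cross-comparison, not in their place.
- Footnote the entire-period table: columns differ in follow-up length, visit frequency and default home dosing (6 of 10 active Q2W doses).
- Footnote the Period 2 table: Q2W patients are newly exposed and in induction; Q4W patients are past induction; placebo remitters and Period 1 dropouts are absent; active-dose-day ascertainment still differs because Q4W home injections are placebo.

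The cost is SAP wording and one re-run of the existing safety programs on a third window, with no new data or visits. The downside is one more descriptive table with wide intervals, which could be over-read if the footnotes are left off.

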### 2.7.1 Adverse events (AEs)

For adverse events and other binary safety variables, crude incidences and exposure-adjusted incidence rate (EAIR) will be derived as described below and summarized in [Table 2-6](#). The crude incidence of treatment emergent adverse events will be summarized by primary SOC and PT.

All AEs and serious adverse events (SAEs) will be listed with “treatment emergent” flag displayed.

**Table 2-6 Overview of analyses on some safety endpoints**

Analysis period	AEs & SPP risks	SAEs	AEs by severity	Study related AEs, death & other significant AEs	Notables (lab/vitals)
Treatment Period 1	• crude incidence	• crude incidence	• crude incidence	• crude incidence	• crude incidence
Entire study period	• crude incidence • exposure-adjusted incidence rate	• crude incidence • exposure-adjusted incidence rate	• crude incidence	• crude incidence • exposure-adjusted incidence rate	• crude incidence

AEs will be summarized by presenting, for each cohort and each treatment group, the number and percentage of subjects having at least one AE, having at least one AE in each primary SOC and having each individual AE (preferred term). Summaries will also be presented for AEs by severity. If a particular AE ‘severity’ is missing, this variable will be listed as missing and treated as missing in summaries. If a subject reported more than one AE with the same PT, the AE with the greatest severity will be presented. If a subject reported more than one AE within the same primary SOC, the subject will be counted only once with the greatest severity at the SOC level, where applicable. AEs by severity will be provided by SOC and AEs by severity and PTs may be provided if required at ad-hoc basis.

The most common AEs reported (at least two cases in any treatment group by SOC and PT) will be presented in descending frequency according to its incidence in AIN457 300 mg Q4W group starting from the most common event. Here the threshold value is set to at least two cases in any treatment group by PT but it may be updated.

Separate summaries will be provided for deaths, SAEs, and other significant AEs leading to discontinuation.

For the legal requirements of ClinicalTrials.gov and EudraCT, two required tables on treatment AEs which are not SAEs with an incidence greater than 5% and on treatment SAEs and SAE

suspected to be related to study treatment will be provided by SOC and PT on the safety set population.

If for a same patient, several consecutive AEs (irrespective of study treatment causality, seriousness and severity) occurred with the same SOC and PT:

- a single occurrence will be counted if there is  $\leq 1$  day gap between the end date of the preceding AE and the start date of the consecutive AE
- more than one occurrence will be counted if there is  $> 1$  day gap between the end date of the preceding AE and the start date of the consecutive AE

For occurrence, the presence of at least one SAE / SAE suspected to be related to study treatment / non SAE has to be checked in a block e.g., among AE's in a  $\leq 1$  day gap block, if at least one SAE is occurring, then one occurrence is calculated for that SAE.

Algorithms for AE date imputations will be provided in [Section 5.1.2](#).

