During Treatment Period 2, subjects who have been on active treatment in Treatment Period 1 receive continued active treatment in the same dosing regimen (secukinumab 300 mg every 4 weeks) until Week 32. This allows the collection of longer term efficacy and safety data beyond 16 weeks of treatment. Subjects who have been on placebo treatment in Treatment Period 1 are switched to active treatment with secukinumab 300 mg every 2 weeks (starting with the regular weekly induction). This enables placebo treated patients to receive active treatment during the trial as well. Furthermore it allows the assessment of efficacy and safety of the 2-weekly dosing regimen in lichen planus. Subjects randomized to the placebo arm who achieve spontaneous clinical remission, which is defined as an IGA of 0 or 1, do not roll over to Treatment Period 2, instead they directly enter the Follow-up Period. The rationale for this is to avoid unnecessary treatment for these patients in Treatment Period 2. An IGA of 0/1 means that there is no or only minor disease activity left, and therefore, no need for a systemic treatment. This design may lead to partial unblinding, since patients who continue into Treatment Period 2 despite having achieved remission by week 16 will be known to have been on active treatment during Treatment Period 1. However, considering the benefit this design brings for placebo-treated patients with spontaneous remission and the fact that this is an early, proof-of-concept study, this limitation can be considered as acceptable.

The secukinumab 300 mg every 4 weeks dosing regimen is given to subjects in the active treatment arm in Treatment Period 1, while the higher dosing regimen, secukinumab 300 mg every 2 weeks, is explored in Treatment Period 2 in subjects switching over from placebo. This

design enables every participating subject to receive active treatment and makes the trial efficient by testing the secukinumab every 4 weeks dosing regimen versus placebo, while additionally giving the opportunity to explore the higher dosing regimen, secukinumab 300 mg every 2 weeks, without having to add an additional treatment arm.

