### **Treatment Period 2:**

Treatment Period 2 starts at the Week 16 visit and covers the time until the Week 32 visit.

Depending on the treatment arm, subjects receive the following treatments:

- **Secukinumab 300 mg Q4W arm:** subjects receive continued treatment with secukinumab 300 mg every 4 weeks plus matching placebo injections to maintain treatment blinding.
- **Placebo for 16 weeks followed by secukinumab 300 mg Q2W arm:** subjects are switched to active treatment with secukinumab 300 mg **every 2 weeks** including a weekly induction starting from Week 16 to Week 20, with the exception of subjects achieving remission by Week 16.

The Week 16 injection is the first injection of Treatment Period 2.

Treatment remains blinded during Treatment Period 2. This means that starting at the Week 16 visit all subjects receive an induction consisting of weekly blinded study drug injections (either secukinumab 300 mg or placebo) at Weeks 16, 17, 18, 19 and 20, followed by blinded study drug injections every 2 weeks.

**The last study drug injection is administered at Week 30.** The end of Treatment Period 2 is Week 32. After Week 32, all subjects enter the Follow-up Period.

Subjects who discontinue study treatment prematurely for any reason other than withdrawal of informed consent should **not** be considered as discontinued from the study. Subjects should continue attending planned site visits and perform study assessments until the last visit of the treatment period during which they discontinue (Week 16 or Week 32).

[figure not shown]
Subjects, whether they are willing to continue attending further study visits or not, should attend the End of Treatment visit (EOT) during which they discontinued (EOT 1 for discontinuation

during Treatment Period 1 and EOT 2 for discontinuation during Treatment Period 2). EOT 1 should be performed 4 weeks after the last dose of study drug, and EOT 2 should be performed 2 weeks after last dose of study drug.

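### Over the entire study period, notable laboratory and vital-sign values are summarised by crude incidence only, although completers have 5 scheduled checks on Q4W and 3 on Q2W, and no other notable rate is planned for Q2W

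*SAP*

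**What the plan says.** SAP Table 2-6 assigns a measure to each class of safety outcome. Over the entire study period, three columns get both crude incidence and an exposure-adjusted incidence rate (EAIR): AEs and risks; SAEs; and study-related AEs, deaths and other significant AEs. AEs by severity and "Notables (lab/vitals)" get crude incidence only. SAP 2.7.3 and 2.7.4.1 add no adjustment for follow-up or number of visits.

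The sentence that introduces the table is broader: "For adverse events and other binary safety variables, crude incidences and exposure-adjusted incidence rate (EAIR) will be derived as described below". It then points the reader to Table 2-6 for the overview.

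For entire-period safety data, SAP Table 2-1 lists the columns "Secukinumab 300 mg Q4W Secukinumab 300 mg Q2W Placebo Any Secukinumab".

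SAP 2.7 fixes what is counted. For visits: "Only those visits that were pre-planned in the protocol will be reported in tables for safety variables". For laboratory and vital-sign data, the window is "any events that happened after first dose of study treatment and on or before last dose +84 days".

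Protocol 4.1 states what the switch to Q2W is for: "Furthermore it allows the assessment of efficacy and safety of the 2-weekly dosing regimen in lichen planus".

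**The concern.** The chance of ever recording a notable value rises with the number of times a subject is checked, whatever the drug does. The entire-period columns cover unequal follow-up: Q4W runs from Week 0, Q2W starts only at Week 16, and placebo ends there. Because only planned visits are tabulated, the visit schedule sets the number of chances to be counted.

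This matters most for Q2W. Safety is presented for Treatment Period 1 and for the entire period, and Q2W does not exist in Treatment Period 1. The by-visit laboratory and vital-sign summaries show change from baseline, not the frequency of notable values. So the only planned notable rate for Q2W sits beside a Q4W rate built on more checks. A reader of that table could take Q2W, which protocol 4.6 describes as a non-approved regimen, to have fewer abnormalities than Q4W when the risks are the same.

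**Working it through.** The plan states no figure for notable values, so there is none to reproduce.

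**Step 1: count the checks.** In protocol Table 8-1, vital signs, haematology and chemistry share the same post-baseline visits for completers: Weeks 8, 16, 24, 32 and 40. Assessments precede the injection (protocol 6.7.2 and 8.4), so the Week 16 check in the switching arm belongs to placebo. I assume that later checks count under the drug then being taken.

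| Column | Checks | k |
|---|---|---|
| Q4W | Weeks 8, 16, 24, 32, 40 | 5 |
| Q2W | Weeks 24, 32, 40 | 3 |
| Placebo | Weeks 8, 16 | 2 |

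Week 40 is inside the window. SAP 1.1 says "The last study drug injection is administered at Week 30", which is Day 211. Day 211 + 84 = Day 295, and Week 40 is Day 281.

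**Step 2: equal risk, independent checks.** P(at least one notable) = 1 − (1 − p)^k. The per-check risk p is not in the documents, so a range is assumed.

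| p | Q4W (k=5) | Q2W (k=3) | Placebo (k=2) | Q4W/Q2W | Q4W/placebo |
|---|---|---|---|---|---|
| 1% | 4.9% | 3.0% | 2.0% | 1.65 | 2.46 |
| 5% | 22.6% | 14.3% | 9.8% | 1.59 | 2.32 |
| 10% | 41.0% | 27.1% | 19.0% | 1.51 | 2.16 |
| 20% | 67.2% | 48.8% | 36.0% | 1.38 | 1.87 |

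At p = 5%, for example, 1 − 0.95^5 = 0.226 and 1 − 0.95^3 = 0.143, and 0.2262/0.1426 = 1.59. The true ratio is 1.0 in every row.

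**Step 3: abnormalities that persist within a subject.** Let the per-check risk vary between subjects as Beta(a, b), with mean p and within-subject correlation ρ: a = p(1/ρ − 1), b = (1 − p)(1/ρ − 1). Then P(none in k) is the product over j = 0 to k − 1 of (b + j)/(a + b + j). At p = 5%:

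| ρ | Q4W | Q2W | Placebo | Q4W/Q2W | Q4W/placebo |
|---|---|---|---|---|---|
| 0.3 | 14.4% | 10.8% | 8.3% | 1.33 | 1.72 |
| 0.5 | 11.0% | 8.9% | 7.4% | 1.23 | 1.49 |

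**Step 4: would a first-event EAIR remove the artefact?** Checks fall every 8 weeks, so time can be measured in check intervals. EAIR = P(event in k checks) / expected intervals to first event or end, where the denominator is the sum over j = 0 to k − 1 of P(none in j). At p = 5%:

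- Independent checks: 0.2262/4.524 = 0.050 for Q4W and 0.1426/2.853 = 0.050 for Q2W; ratio 1.0.
- ρ = 0.3: 0.1435/4.631 = 0.0310 and 0.1079/2.867 = 0.0376; ratio 0.82 (against placebo, 0.73).
- ρ = 0.5: 0.1096/4.687 = 0.0234 and 0.0892/2.876 = 0.0310; ratio 0.75 (against placebo, 0.62).

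Under persistence, EAIR pushes the error the other way.

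**Step 5: does the edge of the window matter?** Table 2-1 speaks of the entire treatment period and Table 2-6 of the entire study period. If Week 40 were left out, the counts would be 4, 2 and 2, and the Q4W ratio at 5% would be 1.90 against either column.

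**The case against.** Several parts of the opposing case stand.

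- **Size.** A reader might infer from the check counts that equal risks will appear 1.6-fold apart (Q4W against Q2W) or 2.3-fold apart (Q4W against placebo). Those ratios need roughly 5% risk per check, independence between visits and full completion. The documents give none of these. Several criteria, such as low pulse, blood-pressure limits and platelets below the lower limit, may well persist within a subject, which shrinks the ratio (Step 3).
- **Placebo.** A reader might also infer that the plan has no fair comparison with placebo. It has one: the Treatment Period 1 table is randomised and concurrent, with two checks in each arm.
- **Direction.** It would be too strong to say that Q2W always looks safer. Protocol 4.1 envisages comparing Q2W in Treatment Period 2 with Q4W in Treatment Period 1. The nearest planned outputs are Q4W over Treatment Period 1 (2 checks) and Q2W over the entire period (3 checks). At 5% and independence these give 9.8% and 14.3%, so Q2W looks worse. The artefact in favour of Q2W belongs to the side-by-side entire-period table.
- **Internal contradiction.** The 2.7.1 sentence defers to Table 2-6, and AEs by severity are also crude only, so the allocation may be deliberate. The mismatch is at most a wording point.
- **Other outputs.** Exposure duration, by-visit changes from baseline and a listing of newly notable vital signs are planned. They alert a reader to unequal follow-up.

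None of this supplies a notable rate for Q2W and Q4W over equal follow-up.

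**Conclusion.** The concern holds for Q4W against Q2W in the entire-period table. With equal true risk, crude incidence is higher for Q4W because it has 5 checks against 3. The artefactual ratio is 1.65 to 1.38 for an assumed 1% to 20% per check with independence, and 1.33 to 1.23 at 5% with correlation 0.3 to 0.5. It exceeds 1 in every scenario examined, but its size depends on assumptions outside the documents and on subjects completing the schedule.

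The placebo column of the same table is distorted too, but the Treatment Period 1 table already answers that comparison. Placebo remitters may add one off-drug check at Week 40, which lowers the placebo ratio slightly (2.22 instead of 2.32 at 5% if 10% remit). The primary endpoint is unaffected. This is a cheap improvement to a descriptive safety display in a proof-of-concept study, and it is worth making because Q2W has no other notable rate.

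**What to change.** 1. Add to SAP Table 2-6 a matched display of notable values over the first 16 weeks on each active regimen: Q4W at Weeks 8 and 16, Q2W at Weeks 24 and 32, two checks each. Label it non-randomised and non-concurrent. State which baseline applies to Q2W, because the SAP safety baseline precedes the first placebo dose and the haemoglobin criterion is a fall from baseline.
2. Footnote the entire-period notables table with the number of scheduled checks per column (5, 3 and 2), and direct the placebo comparison to the Treatment Period 1 table.
3. Optionally add EAIR for notables, which would also bring Table 2-6 into line with the 2.7.1 lead-in. Note beside it that a first-event rate over-corrects when abnormalities persist (Q4W/Q2W about 0.82 at correlation 0.3). It should not replace item 1.

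Cost: SAP wording and one extra table from data already collected. The limits are small numbers (12 planned placebo subjects per cohort, fewer after remitters leave at Week 16) and still no randomised contrast between Q4W and Q2W.
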